6.1.3 Storage Requirements/Stability

The drug product should be stored in a secure location with limited access under controlled temperature conditions of 2-8° C (36° -46° F) in a refrigerator.

6.1.4 Preparation

See http://www.definityimaging.com/pdf/VIALMIX_Users_Guide.pdf, and the package insert for instructions on the use of Vialmix®.

6.1.5 Clinical Safety Summary

See prescribing information on perflutren when used according to its FDA indication (http://www.definityimaging.com/pdf/DEFINITY_US_PI_515987-0117.pdf), and see section 1.3 for a summary of toxicities reported in clinical trials. In addition, the following warnings and precautions are noted in the January 2017 labeling:

Serious Cardiopulmonary Reactions:

Serious cardiopulmonary reactions including fatalities have occurred uncommonly during or shortly following perflutren-containing microsphere administration, typically within 30 minutes of administration. The risk for these reactions may be increased among patients with unstable cardiopulmonary conditions (acute myocardial infarction, acute coronary artery syndromes, worsening or unstable congestive heart failure, or serious ventricular arrhythmias). Always have cardiopulmonary resuscitation personnel and equipment readily available prior to DEFINITY administration and monitor all patients for acute reactions. The reported reactions include: fatal cardiac or respiratory arrest, shock, syncope,

symptomatic arrhythmias (atrial fibrillation, tachycardia, bradycardia, supraventricular tachycardia, ventricular fibrillation, ventricular tachycardia), hypertension, hypotension, dyspnea, hypoxia, chest pain, respiratory distress, stridor, wheezing, loss of consciousness, and convulsions. *Hypersensitivity Reactions:*

In postmarketing use, serious hypersensitivity reactions were observed during or shortly following perflutren-containing microsphere administration including: Shock, bronchospasm, throat tightness, angioedema, edema (pharyngeal, palatal, mouth, peripheral, localized), swelling (face, eye, lip, tongue, upper airway), facial hypoesthesia, rash, urticaria, pruritus, flushing, and erythema have occurred in patients with no prior exposure to perflutren-containing microsphere products. Always have cardiopulmonary resuscitation personnel and equipment readily available prior to DEFINITY administration and monitor all patients for hypersensitivity reactions.

Systemic Embolization of Perflutren in Patients with Cardiac Shunts:

When administering DEFINITY to patients with a cardiac shunt, the microspheres can bypass filtering by the lung and enter the arterial circulation. Assess patients with shunts for embolic phenomena following DEFINITY administration. DEFINITY is only for intravenous administration; do not administer DEFINITY by intra-arterial injection.

Ventricular Arrhythmia Related to High Mechanical Index:

High ultrasound mechanical index values may cause microsphere cavitation or rupture and lead to ventricular arrhythmias. Additionally, end-systolic triggering with high mechanical indices has been reported to cause ventricular arrhythmias. DEFINITY is not recommended for use at mechanical indices greater than 0.8..

6.1.6 Return and Retention of Study Drug

Incomplete vials of perflutren lipid remaining at the completion of the study, or expired perflutren lipid will be destroyed by UNC IDS.

7.0 ADVERSE EXPERIENCES-DRUGS

7.1 Definitions

7.1.1 Adverse Event (AE)

An adverse event (AE) is any untoward medical occurrence (e.g., an abnormal laboratory finding, symptom, or disease temporally associated with the use of a drug) in a patient or clinical investigation subject administered a pharmaceutical product and which does not necessarily have a causal relationship with this treatment. An AE can therefore be any unfavorable and unintended sign (including an abnormal laboratory finding), symptom, or disease temporally associated with the use of a medicinal product, whether or not related to the medicinal product.

Hospitalization for elective surgery or routine clinical procedures that are not the result of an AE (e.g., surgical insertion of central line) need not be considered AEs and should not be recorded as an AE. Disease progression should not be recorded as an AE, unless it is attributable by the investigator to the study therapy.

7.1.2 Suspected Adverse Reaction (SAR)

A suspected adverse reaction (SAR) is any AE for which there is a *reasonable possibility* that the drug is the cause. *Reasonable possibility* means that there is evidence to suggest a causal relationship between the drug and the AE. A suspected adverse reaction implies a lesser degree of certainty about causality than adverse reaction, which means any adverse event caused by a drug.

Causality assessment to a study drug is a medical judgment made in consideration of the following factors: temporal relationship of the AE to study drug exposure, known mechanism of action or side effect profile of study treatment, other recent or concomitant drug exposures, normal clinical course of the disease under investigation, and any other underlying or concurrent medical conditions. Other factors to consider in considering drug as the cause of the AE:

- Single occurrence of an uncommon event known to be strongly associated with drug exposure (e.g., angioedema, hepatic injury, Stevens-Johnson Syndrome)
- One or more occurrences of an event not commonly associated with drug exposure, but otherwise uncommon in the population (e.g., tendon rupture); often more than once occurrence from one or multiple studies would be needed before the sponsor could determine that there is *reasonable possibility* that the drug caused the event.
- An aggregate analysis of specific events observed in a clinical trial that indicates the events occur more frequently in the drug treatment group than in a concurrent or historical control group

7.1.3 Unexpected AE or SAR

An AE or SAR is considered unexpected if the sensitivity and specificity or severity of it is not consistent with the applicable product information (e.g., Investigator's Brochure (IB) for an unapproved investigational product or package insert/summary of product characteristics for an approved product). Unexpected also refers to AEs or SARs that are mentioned in the IB as occurring with a class of drugs or as anticipated from the pharmacological properties of the drug, but are not specifically mentioned as occurring with the particular drug under investigation.

7.1.4 Serious AE or SAR

An AE or SAR is considered serious if, in the view of either the investigator or sponsor, it results in any of the following outcomes:

- Death;
- Is life-threatening (places the subject at immediate risk of death from the event as it occurred);
- Requires inpatient hospitalization (>24 hours) or prolongation of existing hospitalization;*
- Results in congenital anomaly/birth defect;
- Results in a persistent or significant incapacity or substantial disruption of the ability to conduct normal life functions;
- Important medical events that may not result in death, be life-threatening, or require hospitalization may be considered a serious adverse drug experience when, based upon appropriate medical judgment, they may jeopardize the patient or subject and may require medical or surgical intervention to prevent one of the outcomes listed in the definition. For reporting purposes, also consider the occurrences of pregnancy as an event which must be reported as an important medical event.

*Hospitalization for anticipated or protocol specified procedures such as administration of chemotherapy, central line insertion, metastasis interventional therapy, resection of primary tumor, or elective surgery, will not be considered serious adverse events.

Pregnancy that occurs during the study must also be reported as an SAE.

7.2 Documentation of non-serious AEs or SARs

For non-serious AEs or SARs, documentation must begin from day 1 of study treatment and continue through the 30 day follow-up period after treatment is discontinued.

Collected information should be recorded in the electronic Case Report Forms (e-CRF) for that patient. Please include a description of the event, its severity or toxicity grade, onset and resolved dates (if applicable), and the relationship to the study drug. Documentation should occur at least monthly.

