1.4.2 Associated Toxicities

In pre-market clinical trials 1716 subjects were evaluated with activated perflutren lipid. Of the 1716 subjects, 144 subjects (8.4%) had at least one treatment-related adverse reaction. There were 26 serious adverse events and 15 (0.9%) subjects discontinued because of an adverse event.

Nineteen subjects (1.1%) suffered serious cardiopulmonary adverse events including eight deaths. The deaths occurred several days after activated perflutren lipid administration and appear to be related to the course of underlying disease. Of the 11 other serious adverse events, which appeared within 2-15 days of the drug administration, all appeared to be a progression of underlying cardiac and non-cardiac disease.

However, a role for perflutren lipid in the initiation or course of these adverse events cannot be ruled out.

There were 15 discontinuations reported. Nine of these patients were discontinued after the first injection. One patient experienced a hypersensitivity reaction with urticaria and pruritus and all the other patients experienced dizziness, chest pain, dyspnea or back pain. Adverse events (AEs) appeared within 1 – 15 minutes of the drug

administration and were of moderate intensity resolving usually without treatment within minutes or hours after onset.

For all AEs, there were no differences in the overall incidence based on age, gender, or route of administration. The most common events were (% of patients experiencing): headache (2.3%), back and renal pain (1.2%), flushing (1.1%) and nausea (1.0%).

Cardiopulmonary Reactions

In 2007, in response to post-marketing reports of 4 deaths and 190 serious cardiopulmonary reactions, the FDA issued a black box warning for both Definity® and Optison® adding disease state contraindications and a mandatory 30 minute monitoring period following administration in all patients. Following this there have been several large scale safety studies looking into the records of a total of more than 200,000 patients who received one of these contrast agents. In all those studies a composite rate of serious adverse events was calculated to be 1 – 3 in 10,000,[22] compared to gadolinium-based MRI contrast which has an incidence of NSF of 2 – 5 in 100 patients with chronic kidney disease.[23]

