4.2 Enrollment/Recruitment

A total of 60 women will be enrolled to this study. The 60 study subjects will be consecutively recruited from women who are scheduled to undergo core needle or surgical biopsy to have pathological confirmation of malignancy status. Eligible patients will be identified by research staff review in coordination with the UNC Breast Clinic.

Once a patient has been referred, the patient will be approached by a coordinator from Radiology to assess interest in participation.

All eligible women who agree to participate in the study will be asked to come to their scheduled biopsy appointment thirty minutes early to complete the informed consent process.

Review of the consent will take place in the privacy of an exam room, or when possible, a sample consent form will be sent to the patient via email prior to the patient's visit to allow for ample review. Once the patient has consented, women of child bearing potential (WCBP) will be given a urine pregnancy test in order to ensure that they are not pregnant. If a urine pregnancy test shows a result positive for pregnancy, the patient will be excluded from the study per the exclusion criteria because the investigators cannot, in good conscience, expose a fetus to the contrast agent used. Women who consent for the study and are eligible will be escorted by the research coordinator to a dressing room, where the subject will change into a gown.

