4.4 Standard of Care Biopsy

The patient will then undergo her scheduled breast biopsy procedure based on the pre-study diagnostic imaging. The research acoustic angiography imaging will NOT be interpreted prior to the breast biopsy and therefore will not influence any clinical decision concerning the biopsy.

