5.3 Duration of Study

It is anticipated that the total clinical study duration encompassing recruitment, enrollment, and data analysis will take approximately 2 years and will begin in year 4 of the grant. Active patient participation will last approximately 1 visit (consent and 15 minutes imaging).

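### Section 7.2 times non-serious adverse events by calendar date only, so the required data cannot verify drug attribution on the day that contrast and biopsy share

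*Combined protocol and SAP*

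**What the plan says.** **What is recorded.** Section 7.2 lists the items for the electronic case report form: what happened, how severe it was, and then "onset and resolved dates (if applicable), and the relationship to the study drug". Entries are due at least monthly. Section 7.3.2 sets a 24-hour limit for recording a serious event after learning of it. That governs promptness and does not ask when in the day the event began.

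**How causality is judged.** Section 7.1.2 makes it a medical judgment on several factors. The list opens with "temporal relationship of the AE to study drug exposure, known mechanism of action or side effect profile of study treatment", and goes on to other exposures and conditions.

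**How the visit runs.** Under section 4.2, women are asked to "come to their scheduled biopsy appointment thirty minutes early to complete the informed consent process". Contrast imaging comes next, and section 4.4 continues: "The patient will then undergo her scheduled breast biopsy procedure based on the pre-study diagnostic imaging". Section 5.3 confirms the single attendance: "Active patient participation will last approximately 1 visit (consent and 15 minutes imaging"). No interval between the last injection and the biopsy is given.

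**How fast reactions appear.** In its account of subjects who discontinued in the pre-market trials, section 1.4.2 says: "Adverse events (AEs) appeared within 1 – 15 minutes of the drug". These usually resolved within minutes or hours. Sections 1.4.2 and 6.1.5 place serious reactions typically within 30 minutes.

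**How long patients are watched.** Section 4.3.1 gives 15 minutes of monitoring after perflutren; section 1.4.2 gives 30 minutes.

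**The concern.** The protocol leans on a temporal criterion that works in minutes but requires timing in days. Biopsy is itself a recognised source of events: section 1.2 mentions its complications and the anxiety around it, and section 7.3.1 names biopsies as a possible cause of serious events. Dizziness or pain shortly after the visit could plausibly come from either procedure.

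Section 7.2 does record a relationship to the drug, but that field holds the conclusion, not the evidence for it. The Data and Safety Monitoring Committee, which receives safety data under section 9.0, could not test the attribution of a same-day event against the required dates. With documentation due only at least monthly, the sequence might also have to be reconstructed afterwards. What is at stake is how well the safety description can be checked for an agent that section 1.4.1 says is not approved for this use in the breast.

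**Working it through.** The plan states no figure on this point, so the check sets the sections side by side and then adds arithmetic for context.

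**Step 1: what the dates can resolve.** Let D be the visit date.
- Contrast date = D and biopsy date = D (sections 4.2, 4.4 and 5.3).
- For an event that starts that day, onset date = D.
- Onset minus contrast = D − D = 0 days. Onset minus biopsy = D − D = 0 days.

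Both differences are zero whether the event began before or after the biopsy. Section 4.3.1 also speaks of split doses, so there may be more than one injection; a date cannot show which one preceded the event.

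**Step 2: whether another section supplies the times.**
- Sections 7.3.1 and 7.3.2 (serious events): no clock time of onset.
- Section 4.3.1: continuous observation for 15 minutes and a blood pressure reading at 15 minutes. Staff must keep time to do this, but no section requires the injection time to be recorded.
- Section 4.4: no biopsy start time.
- Appendix A: the reader form only.

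**Step 3: whether monitoring keeps the two procedures apart.** No section says that monitoring must end before the biopsy starts. Suppose, as an assumption, that the biopsy begins as soon as monitoring ends, and take 30 minutes as the window in which serious reactions typically appear.
- With 15 minutes of monitoring (section 4.3.1): 30 − 15 = 15 minutes of the window fall after biopsy start.
- With 30 minutes (section 1.4.2): 30 − 30 = 0 minutes.

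The overlap thus depends on two statements that disagree, and on an interval that is not given.

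**Step 4: whether the question is likely to arise.** Inputs: 144 of 1716 pre-market subjects with a treatment-related reaction (section 1.4.2) and 60 women (section 4.2).
- Rate: 144/1716 = 0.0839, matching the stated 8.4%.
- Expected number: 60 × 0.0839 = 5.03.
- Chance of at least one: 1 − (1 − 0.0839)^60 = 0.995.

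This assumes that the pre-market rate applies here. Using the single commonest reaction instead, headache at 2.3%, gives 60 × 0.023 = 1.38 expected and a 75% chance of at least one. Neither calculation says how many events would be attributed wrongly.

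**The case against.** A reader might infer that events are recorded by date and nothing else, and that a perflutren reaction therefore cannot be told from a biopsy effect. The documents do not support that. The same sentence of section 7.2 requires a description, a grade and the relationship to the drug, and a description may state when the event happened. Section 7.1.2 weighs several factors besides timing. A research nurse or physician watches every patient after contrast, so the early reactions described in section 1.4.2 would largely fall under direct observation. Section 11.7 retains source notes, and section 11.8 gives monitors access to original records. The case report form is not among the documents and may already hold time fields; section 7.2 does not forbid them.

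A reader might also infer that a main safety result would be biased. Sections 2.1 to 2.3 contain no safety objective or endpoint, and section 10 plans no safety rate, so there is no planned estimate to bias.

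Nor do the 5 expected women measure misattribution. The 8.4% counts reactions already judged treatment-related, in a different population; this trial excludes active cardiac disease. The 1 to 15 minute onset follows the account of discontinued subjects and should not be read as covering every reaction.

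All of this stands and limits the point. It does not supply what is missing: none of these provisions requires a clock time, so whether the sequence can be checked depends on what staff happen to write down.

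**Conclusion.** The point holds as a gap in data capture. Section 7.2 requires timing by date only, no section requires a clock time for onset, injection or biopsy, and the two procedures share one appointment. For same-day events the required timing data cannot verify the investigator's attribution to the drug, although that attribution can still rest on observation, description and source notes.

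The consequence is limited to the safety description that reaches the safety committee. Sensitivity, specificity, AUC and reader preference are unaffected. The size of any misattribution cannot be derived; all that can be said is that at least one drug reaction is likely among 60 women if the pre-market rate carries over. The conclusion rests on the protocol text, since the case report form was not available. It is a cheap improvement worth making before enrolment, because times not noted on the day may not be recoverable.

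**What to change.** - In section 7.2, require date and clock time of onset and resolution for any event on the visit day. Apply the same rule to serious events under section 7.3.
- On the visit form, record the clock time of each perflutren injection, the end of study imaging and the start of the biopsy.
- In the safety listing for the committee, show each same-day event as starting before or after the start of the biopsy.
- Separately, reconcile the 15-minute monitoring statement in section 4.3.1 with the 30-minute statement in section 1.4.2. The documents do not settle which applies.

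The cost of the first three changes is a few extra form fields and one column in a listing. They add no procedure, visit or patient, and leave the statistical analysis in section 10 as it is. If the case report form already captures these times, only the protocol text needs to change.

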7.3 SAEs or Serious SARs

7.3.1 Timing

After informed consent but prior to initiation of study medications, only SAEs caused by a protocol-mandated intervention will be collected (e.g. SAEs related to invasive procedures such as biopsies, medication washout, or no treatment run-in).

For any other experience or condition that meets the definition of an SAE or a serious SAR, recording of the event must begin from day 1 of study treatment and continue through the 30 day follow-up period after treatment is discontinued.

7.3.2 Documentation and Notification

These events (SAEs or Serious SARs) must be recorded for that patient within 24 hours of learning of its occurrence.

7.3.3 Reporting

IRB Reporting Requirements:

- UNC will submit an aggregated list of all SAEs to the UNC IRB annually at the time of study renewal according to the UNC IRB policies and procedures.
- The UNC-IRB will be notified of all SAEs that qualify as an Unanticipated Problem as per the UNC IRB Policies using the IRB's web-based reporting system (see section 8.2) within 7 days of the Investigator becoming aware of the problem.

Pregnancy

Pregnancies and suspected pregnancies (including a positive pregnancy test regardless of age or disease state) of a female subject occurring while the subject is on study should be recorded as SAEs. The patient is to be discontinued immediately from the study. The female subject should be referred to an obstetrician-gynecologist, preferably one experienced in reproductive toxicity for further evaluation and counseling.

The Investigator will follow the female subject until completion of the pregnancy, and must document the outcome of the pregnancy (either normal or abnormal outcome). If the outcome of the pregnancy was abnormal (e.g., spontaneous or therapeutic abortion), the Investigator should report the abnormal outcome as an AE. If the abnormal outcome meets any of the serious criteria, it must be reported as an SAE.

8.0 UNANTICIPATED CONCERNs

8.1 Unanticipated Adverse Device Effect (UADE)

The investigational device exemption (IDE) regulations define an unanticipated adverse device effect (UADE) as "any serious adverse effect on health or safety or any life-threatening problem or death caused by, or associated with, a device, if that effect, problem, or death was not previously identified in nature, severity, or degree of incidence in the investigational plan or application (including a supplementary plan or application), or any other unanticipated serious problem associated with a device that relates to the rights, safety, or welfare of subjects" (21 CFR 812.3(s)).

8.2 Unanticipated Problems (UP)

As defined by UNC's IRB, unanticipated problems involving risks to study subjects refers to any incident, experience, or outcome that:

- Is unexpected (in terms of nature, severity, or frequency) given (a) the research procedures that are described in the protocol-related documents, such as the IRB-approved research protocol and informed consent document; and (b) the characteristics of the subject population being studied;
- Is related or possibly related to a subject's participation in the research; and
- Suggests that the research places subjects or others at a greater risk of harm (including physical, psychological, economic, or social harm) related to the research than was previously known or recognized.

